## List of Abbreviations:

AE	Adverse Event
ADE	Adverse Device Effect
AI	Adult Incontinence
CER	Clinical Evaluation Report
CRF	Case Report Form
eCRF	Electronic Case Report Form
GCP	Good Clinical Practices
H&P	Habits and Practices
ICH	International Conference on Harmonization
IRB	Institutional Review Board
MDR	Medical Device Regulation
ISO 14155	Clinical Investigation of Medical Devices for Human subjects GCPs
ISO 14971	Medical Devices - Application of Risk Management to Medical Devices
NJ EU	Ninjamas Europe Overnight Pant
[REDACTED]	[REDACTED]
pH	Potential Hydrogen
P&G	Procter & Gamble
QoL	Quality of Life
SAE	Serious Adverse Event
SADE	Serious Adverse Device Effect
[REDACTED]	[REDACTED]
TMF	Trial Master File

***Clinical Trial Protocol*****1. Introduction**

Ninjamas Europe (NJ EU) is an absorbent disposable single-use underwear pant developed for children suffering from nocturnal enuresis (nighttime bedwetting). The NJ EU absorbent underwear pant helps manage and contain urination gushes at night for up to 12 hours. It is not intended to treat or cure nocturnal enuresis. It is a non-invasive device and intended for external application on intact skin. It is a simple non-active device (without electronics or batteries) that is very easy to use. No specific training is required to use this product. It is available in 2 sizes: Size 7 for children aged 4-7 (17-29 kg) and Size 8 for children aged 8-12 years (27-43kg).

Since nocturnal enuresis in the age group 5 years and above is considered a medical condition in Europe, this absorbent underwear pant is regulated as a Class 1 medical device in the EU. This clinical trial will be part of the body of clinical evidence needed to support the Medical Device Report, which is required to market this absorbent product as a nocturnal enuresis management tool for children age 4-12 years in the EU.

There are several ways to manage nocturnal enuresis in children. This clinical trial will focus on the first option only:

- Absorbent underwear to manage urine loss without treating it.
- Bed mats absorb urine and prevent the mattress from getting wet but do not keep the child's clothing and bed sheets from getting wet.
- Fluid and diet restriction prior to bedtime.
- Waking the child at specific times during the night to go to the bathroom.
- Bladder training or retention control training, where the child is trained to hold the urine as long as possible in order to increase bladder capacity.
- Rewards and star charts to encourage nights without bedwetting.
- Wetness alarms (bells or vibrations that wake the child when urinating).
- Desmopressin (synthetic version of anti-diuretic hormone).
- Anticholinergic medicine (e.g., Oxybutynin) reduces the number of involuntary bladder contractions and has a relaxant effect on the smooth muscle of the bladder. This decreases the urge to pass urine and allows the bladder to hold more urine.
- Tricyclic drugs - work the same as Oxybutynin but are only used in cases where other drugs are not working. The need for close follow up and the potential for serious cardiac consequences with overdose mean they are considered for use in specialist centers only.
- Psychological treatment.

The P&G company has a 20+ year history of baby diaper clinical data (0-36 months) to show that our diaper and pant technology is safe to use and effective for managing urine gushes in a baby and toddler population. The P&G company also has adult (18+ years) female incontinence products in the EU market, including absorbent heavy incontinence pants, that are classified as Class 1 Medical Devices, which were demonstrated to be safe to use and effectively manages urine gushes of adults as seen in the statement of compliance from the CER report [1].

[1] P&G markets a training pant (BabyDry Pants S7) in the EU. Based on the Post Market Safety Surveillance data of similar products in the EU and US market (BabyDry Pants, FemCare AI Pants, [REDACTED]), we have reason to believe that the NJ EU product will have no safety

[figure not shown]
related issues when used as an overnight pant for children aged 4-12 years, based on skin and health related AEs. [2]

[REDACTED] the design of the P&G Adult Incontinence [REDACTED] pants and the [REDACTED] pants for babies and toddlers are comparable to that of the NJ EU [REDACTED] pant for bedwetting children, and there is a reason to believe that the NJ EU [REDACTED] pant meets all safety and product performance requirements [REDACTED]

[REDACTED]. This clinical trial provides helpful technical data to bridge to the existing body of evidence clinical data from adult and baby clinical trials and gather clinical safety in-use data for this specific population of children, with a different gush volume than adults and babies and using the products only during night.

Looking at the prevalence of nocturnal enuresis, this condition is more likely among younger children (size 7, or S7, which is designed for children aged 4-7) than older children (size 8, or S8, which is designed for children aged 8-12). The graphs below show data from publications on nocturnal enuresis for UK [3] and USA [4] respectively.

Figure 1 & 2: Prevalence of Nocturnal Enuresis for UK [1] and USA [2].

[figure not shown]

This clinical trial will therefore focus on the more representative S7 group. Reasons for choosing this group include:

1. This group will be easier to recruit with approximately 10-25% of the population suffering from nocturnal enuresis at age 4-7, compared to only 1-5% of the population at age 8-12. In addition, the willingness of younger children to participate in a bedwetting clinical trial where the parent needs to do measurements in the pant area will be higher than for older children, who may not want the parent in the room when they remove their pant.
2. Traditionally children are not considered for treatment of bedwetting until age 7. Over the age of 7 the child is usually treated with drug therapy to reduce urine production at night.
3. The S7 and S8 NJ EU pants have the same design, with S8 having a more absorbent capacity and a bigger fit.

[REDACTED]

[REDACTED]

5. Younger children are more likely to wait for a parent to assist with dressing and will therefore wear the wet pant longer than an older child, who is more likely to remove the pant themselves. Younger children also have a higher risk of feces on the skin (which is an irritant for the skin) as they are not well-practiced in wiping themselves clean after visiting the toilet. Therefore, the S7 group has more risk of developing rash from wet pants than the S8 group, because their skin is wet longer and any feces resting on the skin can result in compromised skin and rash in the pant area.

Our focus will be on children with monosymptomatic enuresis i.e., enuresis in children without any other lower urinary tract symptoms (e.g., increased frequency, daytime incontinence, urgency, genital, or lower urinary tract pain) and without a history of bladder dysfunction.

This clinical trial will accept children with both primary and secondary enuresis. Primary enuresis means the child has never had a dry period at night. Secondary enuresis means the child developed nocturnal enuresis after being dry for a period of at least six months.

This clinical trial will be a 6-week, in-home clinical trial to understand the safety, performance, and impact on skin of the NJ EU pant compared to the child's currently used absorbent pant or diaper product.

## 2. Objectives

The primary objective of this clinical trial is to confirm the in-use tolerability of the Ninjama EU overnight pant product, in the target population of bedwetters aged 4-7 years, based on a body of evidence from clinical assessments of skin, adverse events and parent/child perception data. This data will be part of the clinical evidence in the Clinical Evaluation Report needed to market this product as a Class 1 Medical Device in the EU, confirming that the product is safe to use and performs within its intended purpose.

The secondary objective is to understand the clinical benefit of the NJ EU overnight pant product in a bedwetting population aged 4-7 years, based on [REDACTED] waking up in a dry bed, via collecting H&P and parent/child perception data in diaries and end-of-use questionnaires.

[REDACTED]

## 3. Investigational Plan

### 3.1 Clinical Trial Design

This will be a single center, single blinded (sponsor's team will be blinded to the product codes), randomized, cross-over, IRB-Approved, in-home clinical test design over 6 weeks, with two usage periods of 3 weeks each. During one period the child will maintain usage of their usual absorbent night pant/diaper and during the other usage period they will use the NJ EU absorbent pant. We will track habits and practices that may impact skin health and product performance as well as medication use and Adverse Events/ Adverse Device Effects (AEs /ADEs). Children will be asked to wear either their own pants or the test pants exclusively at night and parent/legal guardian will be asked to collect data in the evening before bed and in the mornings after getting up.

Parent/Legal Guardian will be trained to execute the measurements on their own child for the following reasons:

1. Children this age are usually told not to let strangers touch them in the genital and buttock area, so we want to avoid telling kids it is OK in this case. We will ensure that the child is comfortable to participate in this clinical trial and can at any time end their participation in this clinical trial should they feel uncomfortable.
2. Due to COVID restrictions, clinical trial personnel should minimize close contact with panelists as much as possible, especially with children under 5 years of age, who cannot be vaccinated. We will therefore ask the trained parent/legal guardian to do the measurements on his/her own child/ren. Children can stop the study procedures at any time if/when they feel uncomfortable.

This clinical trial is designed to track the following:

- general safety (AEs and ADEs),  
[REDACTED]
- assess fit and performance of the overnight pant products (fit images, leaks, [REDACTED])

The following table shows which endpoints will be measured at which time and where on the child:

Endpoint	When Measured	Where Measured
Leaking & Pant Fit	Before pant removal	Waist front and back, crotch area, leg cuffs
Child skin irritation perception	Directly before removing pant	Entire pant area
AE, ADE, [REDACTED]	Observed all the time and reported twice a day	Observe child and pant

[REDACTED] Leaking and Pant Fit: Mobile phone images of the pant on the child will be collected by the parent/legal guardian at home [REDACTED]

- Child Perception: Child will be asked simple yes/ no questions to determine if they feel irritation [REDACTED]. If yes, the parent/legal guardian will ask the child to point to location where they feel the irritation [REDACTED].

- [REDACTED]

- [REDACTED]

Up to 30 children (approximate split of 15 males and 15 females) who meet inclusion/exclusion criteria will be enrolled in the clinical trial. S7 children will be enrolled in this clinical trial because nocturnal enuresis is most prevalent in children aged 4-7 and the pant design for S7 and S8 products are similar. Therefore, the data generated for the S7 population can be used to support the S8 population. Children for this clinical trial will be enrolled by North Cliff Consultants in Cincinnati, USA. Eligible subjects will be bedwetters who have wet the bed at least once a week or more over the past 3 months. The children should be accustomed to wearing an absorbent pant product overnight. They will be asked to use their own overnight pant every night for 3 weeks of the clinical trial and will be asked to use the NJ EU test pant every night for the other 3 weeks of the clinical trial. The order of the NJ EU product and own product will be randomized. Parents will

be asked to refrain from using wet wipes to clean the child's skin for the duration of the clinical trial (no test wipes will be provided).

If a subject drops out of the clinical trial, they will not be replaced, due to the short duration of the clinical trial.

Once qualified, parent/legal guardian will be asked to pick up the equipment [REDACTED] [REDACTED] from North Cliff Consultants. They will receive training on how to handle the equipment and how to complete the questionnaires. Parent/legal guardian will be required to begin with the clinical trial after the training session. They will be given 2 days to practice [REDACTED] before data is officially collected for the clinical trial.

Parent/legal guardian will be instructed to complete a digital questionnaire twice daily (once in the morning before removing the used pant and once in the evening when applying the fresh pant) [REDACTED]. This will include taking four photos of the child wearing the pant (front, back and both hips) [REDACTED].

[REDACTED]. It includes capturing adverse events and compliance questions. Subjects will also be asked to complete a H&P questionnaire at the clinical trial start and at the end of each 3-week period and they will also be asked to complete an after-use questionnaire.

This clinical trial will be submitted for IRB/ethics review.

### **3.2 Clinical Trial Procedures**

#### **3.2.1 Visit 1 – Enrollment and Training (on Site)**

1. On the day of their appointment, a parent/legal guardian will be asked to come to the clinical site together with their participating child.
2. Parent/legal guardian will be instructed to read the Informed Consent document but not sign until they meet with clinical personnel. They will be given the opportunity to have any questions answered. They will be asked to sign two copies of the Informed Consent in the presence of clinical personnel. After verification of a legible signature, the parent/legal guardian will be instructed to keep one signed copy of the Informed Consent. The clinical site will keep the other copy.
3. Parent/legal guardian will be asked for demographic information and inclusion/exclusion criteria to determine if their child is eligible to participate in the clinical trial. Children will be weighed on a bathroom scale and have their body length, waist circumference (lying down and standing), thigh circumference and hip circumference measured by the parent under the supervision of a clinical staff member. The participating child must be present, so clinical personnel can verify the age, weight, Fitzpatrick scale and general health of the child. The child will also be asked to try on one of the overnight test pants to ensure proper fit. If eligible, parent/legal guardian will be asked about the typical habits and practices of their child [REDACTED].
4. The subjects will be asked to bring along a packet of their currently used overnight pant product so the test site can verify that this product brand qualifies as one of the allowed "own product brands" (current marketed disposable or reusable absorbent overnight pants/diapers or training pants/diapers). The brand name and lot code of this product will be documented.

5. Subjects will be randomized to use either their current product, or, be distributed the NJ EU product, for the first 3-week test period of the study. If randomized to start with the NJ EU product, they will be asked to return any unused product at the end of the 3 weeks. If randomized to start with their own product, they will be instructed to use this brand exclusively for the 3-week test period. They will not be allowed to switch brands during this period.
6. Subjects will be instructed to use an overnight pant every night for the duration of the study.
7. The use of skin products like lotions, oils, powders, creams, sunscreens, wet wipes and moisturizing bubble baths will not be allowed to be used in the pant area and thighs, unless needed for medical reasons. Use of these skin preparations will be captured in the daily questionnaire [REDACTED]  
[REDACTED].
8. After enrollment, parent/legal guardian will receive the following items:  
[REDACTED]  
[REDACTED]
  - [REDACTED]
  - Two coin-cell batteries as back-up
  - [REDACTED])
  - Kitchen scale (balance) with USB charging cable
  - [REDACTED]
  - Measuring tape
  - [REDACTED]
  - Written subject instructions
9. Parent/ legal guardian will participate in a training session on the following:
  - a. Review of [REDACTED] questionnaire
  - b. How to take photos using mobile phone [REDACTED]
  - c. How to assess rash, imprints/marks on the skin
  - d. [REDACTED])
  - e. [REDACTED]
  - f. [REDACTED]
  - g. [REDACTED]
  - h. How to weigh the pant
10. [REDACTED]  
[REDACTED]
11. Parent/legal guardian will be asked to begin completing the questionnaire (2x/day) for 45 days. The first 2 days will be considered practice days and data from day 1 and 2 will be considered non-evaluable.

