### 3.2.2 During the 6-Week at Home Clinical Trial

1. Parent/legal guardian will be asked to complete the questionnaire 2x daily for 45 days.
  - Once in the evening when applying the fresh night pant
  - Once in the morning when removing the used pant
2. In the evenings they will be asked to apply a fresh pant and wait ~15 minutes, before doing images, [REDACTED] and skin assessments. In the mornings, they will be asked to take the images before they remove the pant and then remove the pant to do skin assessments. [REDACTED]  
[REDACTED]
3. [REDACTED] the questionnaire has several questions to check compliance and ADEs and AEs throughout the clinical trial [REDACTED]  
[REDACTED]
4. Parent/ legal guardian will be asked to [REDACTED] assess skin [REDACTED] rash, [REDACTED], enter pant wear time and weight, assess leaking, and take images of the pant fit on the child in standing position. If the overnight pant did leak, they will be asked to take an image of the wet stain on the pajama pant in the crotch area as well as front, back or sides in a standing position, so we can see the location and size of the leak.
5. [REDACTED]  
[REDACTED]  
[REDACTED]
6. [REDACTED]  
[REDACTED]  
[REDACTED]
7. [REDACTED]  
[REDACTED]  
[REDACTED]
8. The parent/legal guardian will be called via phone or video chat after the 2 practice days to provide feedback after monitoring their data. Throughout the

clinical trial the submitted data will be monitored and subjects will be contacted at least once per week (either during planned study visits or remote phone/video calls) so the study site can give feedback, check on progress, track lot codes of new purchased products and answer questions throughout the clinical trial.

[REDACTED]

9. The following topics will be assessed by the site or sponsor based on the [REDACTED] responses and will be discussed during the weekly phone calls:
  1. Resolution/Tracking of any AEs or ADEs
  2. Resolution/Tracking of Medication Use
  3. Feedback on data quality and study progress
  4. Compliance (reasons for missed questionnaires or study instructions not being followed)
  5. [REDACTED]
  6. Track lot codes of new purchased own products
  7. Answer questions the subjects may have

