### 3.2.5. Clinical Trial Schedule of Events

Procedure	Visit 1: Enrollment and Training	Visit 2: Product pick up and instrument check (3 weeks after visit 1)	AT HOME: Clinical Trial Mode Days 1 – 45	Weekly Phone Calls (after 2 days and then weekly, if no study visits planned for that week)	Visit 3: Final Visit
Informed Consent	X				
Demographics	X				
Inclusion/Exclusion	X				
Anthropometry	X				
Subject Instructions (training session)	X				
H&P Questionnaire [REDACTED]	X				
Randomization	X				
Product Distribution (per randomization)	X	X			
Compliance/ AE Resolution		X	X	X	X
Twice Daily Questionnaire [REDACTED] (photos and measurements)			X		
[REDACTED]		X			X
Subject Accountability					X

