### 3.3.2 Exclusion Criteria

Subjects are ineligible for enrollment if the parent/legal guardian responds positively ("Yes") to any of the following questions:

- EXCL01:** Does your child have any acute or chronic skin conditions (excluding skin rash) in or around the pant area?
- EXCL02:** Does your child currently have (or have a history of) any significant illness or chronic medical condition (SITE: that in the opinion of the investigator may negatively impact child's health and/or clinical trial results, for example medications to treat nocturnal enuresis, antibiotics, antihistamines, anti-inflammatory medications, corticosteroids, medications to treat yeast infection or similar)?
- EXCL03:** Is your child currently using any medications? (SITE: that in the opinion of the investigator may negatively impact child's health and/or clinical trial results)?
- EXCL04:** Does your child currently wear absorbent products during the day?

**EXCL05:** Does your child suffer from any other lower urinary tract symptoms (e.g., increased frequency, daytime incontinence, urgency, genital, or lower urinary tract pain) or a history of bladder dysfunction?

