#### **7.5.1 Adverse Event and Adverse Device Effect Reporting**

[REDACTED] the parent/legal guardian will be asked twice daily about their child's health and medication intake. Based on the information provided, Sponsor and PI will determine if it is appropriate to record as an Adverse Event or Adverse Device Effect and will contact the parent/legal guardian for more information. Such an occurrence does not necessarily have to have a causal relationship with product use. Due to the nature of this clinical trial, skin irritation in the pant area (diaper rash) will not be documented as an Adverse Event or Adverse Device Effect given it is one of the end points of interest for the clinical trial. However, if a skin reaction occurs in the pant area which causes the parent/legal guardian to seek medical attention, outside the normal follow-up given to the child within the clinical trial, this will be documented and followed in the same manner as other Adverse Events or Adverse Device Effects.

[figure not shown]
The Investigator or designee will review each Adverse Event Report and complete the form based on the following decision charts:

*Chart 1: Categories of ADE and AEs*

Adverse events	Non-device-related	Device- or investigational procedure-related	
Non-serious	Adverse event (AE) a (3.2)	Adverse device effect (ADE) c (3.1)	
Serious	Serious adverse event (SAE) b (3.45)	Serious adverse device effect (SADE) (3.44)	
		Anticipated	Unanticipated
		Anticipated serious adverse device effect (ASADE) c (3.1, Note 1 to entry)	Unanticipated serious adverse device effect (USADE) (3.51)

a Includes all categories.  
b Includes all categories that are serious.  
c Includes all categories that are related to the device or the investigational procedure.

Chart 2: AE categorization flow chart

The Investigator or designee will review each Adverse Event Report and complete the form based on the following definitions:

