**Revised Wording:**

5. Subjects will be randomly assigned to begin with either their own product or the test product per a stratified randomization plan that utilizes randomization strata based on child's sex (male or female) and age group (4-5 years or 6-7 years). Randomization will be done so approximately 50% (n=16) of subjects will begin with their own product and approximately 50% (n=16) of subjects will begin with the test product. Product sequence will be assigned from a computer-generated randomization program provided by the Sponsor. The sequence of numbers used for the randomization will be 3-digit consecutive numbers whose first digit will not be the same as the 4-digit sequence used for subject identification (e.g., 301).

**Attachment R: COVID or Weather Impact to Clinical Trial Procedures****3.2.1 Visit 1A – Enrollment (Virtual for Covid)****Original Wording:**

5. Subjects will be randomized to one of two usage periods, either starting with their own current product or starting with test product.

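### The two-day practice rule makes no exception for rash or child-reported irritation, so about half of the children probably contribute no evaluable skin data from their first one to two nights in the test pant.

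*Combined protocol and SAP*

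**What the plan says.** Parents complete a questionnaire twice daily for 45 days. On the opening days, section 3.2.1, item 11 states: "The first 2 days will be considered practice days and data from day 1 and 2 will be considered non-evaluable". Section 3.1 likewise places two practice days ahead of official data collection; what is practised is redacted there.

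Product order is randomized and product is handed out at Visit 1 (sections 3.2.1 and 3.2.5). Section 3.1 adds: "Parent/legal guardian will be required to begin with the clinical trial after the training session". Under Amendment 1, "approximately 50% (n=16) of subjects will begin with the test product", and the same number begin with their own product. The schedule puts Visit 2, where products are switched, three weeks after Visit 1. No practice days are stated after the switch.

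Rash is graded in the diary. In the evening parents "apply a fresh pant and wait ~15 minutes" before the skin assessment. The visible schedule shows no skin grade at Visit 1. A child with rash may enrol, because EXCL01 asks: "Does your child have any acute or chronic skin conditions (excluding skin rash) in or around the pant area".

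Section 7.5.1 says that "skin irritation in the pant area (diaper rash) will not be documented as an Adverse Event or Adverse Device Effect", because rash is an endpoint; the exception is a reaction for which the family seeks outside medical attention. The SAP (Attachment B) says that the sponsor will document how non-evaluable observations are handled before the analysis.

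**The concern.** The primary objective is in-use tolerability of the new pant, and first contact is one of the times when a skin reaction could show. For children who start on the test pant, first contact falls in the practice window. For children who start on their own product, it falls after Visit 2, where every night counts. The same test-pant nights are therefore evaluable in one sequence and not in the other.

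Two rules combine to leave the gap. Rash is kept out of adverse event reporting because it is an endpoint, yet on days 1 and 2 it is not evaluable as an endpoint either. A mild rash that clears within those days appears in no output that the plan describes.

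The entry grade is also affected. The day-1 evening grade is the nearest thing to a baseline in the visible text, and it is non-evaluable in both sequences. Children who start on their own product still have evaluable Period 1 grades before they meet the test pant. Children who start on the test pant have none, so a rash graded on day 3 cannot be told apart from one that the child brought in.

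**Working it through.** **Inputs from the documents**
- About 32 children, 16 per sequence (Amendment 1). Check: 32 × 0.5 = 16. The total has no statistical derivation (section 4.2), so there is no power figure to reproduce.
- Diary of 45 days; two periods of 3 weeks; days 1 and 2 non-evaluable.

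**Assumption.** The assigned product is worn on days 1 and 2. It is inferred from randomization and distribution at Visit 1 and the start of use after training.

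**Calendar.** The evening of day 1 to the morning of day 45 is 44 nights, and 44 = 2 + 42 (2 × 21).
- If the practice nights are additional to the two periods, each sequence has 21 evaluable test-pant nights: wear nights 3 to 23 for test-first children, wear nights 1 to 21 for own-first children.
- If Visit 2 falls exactly 3 weeks after Visit 1, test-first children have 21 − 2 = 19 evaluable test-pant nights, and own-first children have 21 to 23.

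The first test-pant nights are lost on either reading.

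**Nights lost**
- First-two-night test-pant child-nights: 32 × 2 = 64. Non-evaluable: 16 × 2 = 32, or 50%.
- All test-pant nights: 16 × 23 + 16 × 21 = 704; 32/704 = 4.5%.
- If only records dated day 1 or 2 are dropped and the first record is the day-1 evening, the grade on the morning after night 2 is dated day 3 and counts. One night per child is then lost: 16 child-nights.
- Own-first children lose 16 × 2 = 32 own-product nights, so the totals by product are equal.

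**Worst case: no reaction lasts to an evaluable grade**
- Zero events seen, two-sided 95% upper limit 1 − 0.025^(1/n): n = 16 gives 20.6%; n = 32 gives 10.9%.
- Chance of seeing at least one reacting child, 1 − (1 − p)^n. The risks p are assumptions; the documents give none.

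| Assumed risk p | 16 children | 32 children |
|---|---|---|
| 2% | 28% | 48% |
| 5% | 56% | 81% |
| 10% | 81% | 97% |

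**With persistence.** Assume onset on night 1 or 2 with equal chance, and a constant nightly chance c that the rash continues (mean duration 1/(1 − c) nights). With two nights lost, a test-first child's reaction is visible if it is present on night 3, with probability v = (c + c²)/2. Detection is 1 − (1 − p)^16 × (1 − pv)^16. At p = 5%:

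| c | Mean duration (nights) | v | Detection |
|---|---|---|---|
| 0 | 1 | 0 | 56.0% |
| 0.5 | 2 | 0.375 | 67.5% |
| 0.7 | 3.3 | 0.595 | 72.9% |
| 0.9 | 10 | 0.855 | 78.1% |
| all nights kept | – | 1 | 80.6% |

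**Effect on averages.** Assume rash on 20% of ordinary nights and 40% of the first two test-pant nights. The average excess over own product is 1.8 points with all nights and 0.9 to 1.0 points on evaluable nights.

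**The case against.** A practice window fixed in advance is a reasonable choice when lay parents do the grading, and the site reviews the early records: "The parent/legal guardian will be called via phone or video chat after the 2 practice days". The SAP also leaves the handling of non-evaluable observations to a sponsor document written before analysis, and Amendment 1 provides for an evaluability meeting with coded products. This supports keeping the rule for the main comparison. It does not restore the data: the phone call gives feedback and is not an analysis record, and nothing in the plan says that day 1 and 2 skin grades will be reported.

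A reader might infer that safety data in general are lost. The documents do not support that. Health questions run daily after the initial visit (section 7.5), adverse event checks run throughout (section 3.2.2, item 3), and product-related events are summarised for both periods (Attachment B, General Safety). Medically attended skin reactions are recorded (section 7.5.1), and reasons for stopping are documented (sections 3.5.1 and 7.5.1). Only rash without outside medical attention and child-reported irritation remain exposed.

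A reader might also infer that the rule tilts the comparison between products. Own-product nights are lost in equal number, and randomized order balances carried-in rash on average. Missing early reactions would favour the test pant, while entry rash attributed to it would count against it, so the net direction is unknown. The rule could also create an apparent period difference in the plotted means, but under the assumed rash rates it is only 1.7 to 1.9 points. Treating 16 × 21 nights per period as independent, its standard error is already about 3.1 points, and clustering within child would widen it.

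Finally, the practice-day product is not stated, and nearby text is redacted. If every child practised in their own product, no test-pant nights would be lost. Redacted items could also hold a Visit 1 skin measure or scoring rules that bear on this.

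**Conclusion.** The point holds for parent-graded rash and child-reported irritation. If the assigned product is worn on days 1 and 2, following the plan removes the first one to two test-pant nights from the evaluable skin data in about half of the children, and leaves test-first children with no evaluable skin grade before the test pant. The defect is missing first-exposure data and unequal windows by sequence, not an imbalance between products.

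The size is modest: at most half of the first-two-night test-pant exposure, and a small effect on overall averages. The 20.6% limit and the 56% detection figure apply only if every reaction in test-first children clears before an evaluable grade; longer-lasting reactions narrow the gap. All detection figures rest on assumed risks and durations. The change is still worth making, because the trial is small, tolerability is its primary objective, and the records are already collected.

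**What to change.** Keep the practice-day rule for the main comparison and state in the SAP that:

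1. rash and child-reported irritation from days 1 and 2 are listed by product for the ITT population, beside the adverse event and adverse device effect summary, and labelled as practice-day data;
2. the day-1 evening rash grade is kept as a flagged entry grade, with a note that it is taken about 15 minutes after the first pant is applied;
3. one sensitivity analysis leaves out the first two nights of both periods, so that like nights are compared.

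Also state in the protocol which product is worn on the practice days.

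The cost is a few lines of SAP text, one listing and one extra analysis, with no added children, visits or measurements. The drawback is that parent grades on these days are noisier because parents are still learning, which is why the listing needs its label.
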